- We believe that this study will generate an estimate of the effect that can be used to inform the development of randomized controlled studies (RCTs).
 - This study will also generate RCTs examining the use of the Oculus VR as a form of stroke rehabilitation that is scalable to the participant's home setting.
 - There are few studies that have examined the role of caregiver engagement on the success of remote stroke rehabilitation.
- The caregiver will be encouraged to use Caregiver Cues (Appendix D) as this will help the caregiver to engage with the participant using encouragement or positive cues to the stroke participants to support them during the session.
- The therapist or RA (who will be trained by the therapist) who is conducting the session will use the Therapist Guided Cues (Appendix E) to guide the stroke participant with problem solving and planning for performing home exercises that will be provided to the participant at the first session.
- The data we obtain from caregivers and stroke survivors (dyads) will inform future studies that examine ways to best support the dyads to improve stroke rehabilitation outcomes and reduce stress in the caregivers. (See Appendix F)

Statistical Analysis

- To address S.A.1., feasibility, usability, and acceptability of the Oculus VR headsets for upper extremity and cognitive therapies will be analyzed as follows: Feasibility: Assessed from the number sessions attended and time spent using the Oculus VR. The minimum number of sessions expected for a user are 2 per week (8 sessions) and the minimum time spent playing Job Simulator is 1 hour per week (4 hours) through the end of the study. Descriptive statistics of the participation rates and measures including frequencies, median and interquartile ranges for sessions attended and time spent using the game. Usability: Descriptive statistics for demographic and clinical data and participant scores on the SUS and PQ will be calculated. (See Appendix G and H) We will refrain from using inferential statistics since this is a pilot study and hypothesis testing is not the objective. Acceptability: Descriptive statistics for scores on the SSQ will be calculated at baseline and after each session (See Appendix I). We will examine the trend of symptoms for each participant.)

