- To address S.A.2. As part of standard of care, we will calculate change in arm and cognitive scores for each stroke participant from the following tests: MoCA, FM, and ARAT. (See Appendix J, K, and L) After inspection of the distribution, either the paired t-test or the nonparametric Wilcoxon signed rank test will be used to evaluate the significance of the difference score. However, statistical inference is not the primary interest of this pilot study. The effect size provided by Cohen's d measure, i.e., the standardized difference of mean score, will provide a preliminary measure of the effectiveness of Oculus VR in this pilot study. Similarly, standardized differences in the BSFC-s scores will provide the effect sizes for the change in caregiver burden.
- To address S.A.3., interview data will be analyzed following methods for thematic analysis.^{34,35} Using a qualitative data analysis program, Atlas.ti,³⁶ 2 researchers will review transcripts to gain a sense of the whole, identify codes, categories, and generate higher order themes to describe

the role of caregiver engagement during the session. Reasons for non-participation will be obtained from those eligible participants who decline participation. Unacceptable components and reasons for non-participation will be considered in the planning and designing of future trials.

Outcomes

- Upon completion of these aims, the expected outcomes are to develop randomized control trials (RCTs) to determine the effectiveness of the Oculus VR for stroke rehabilitation. We anticipate using the information from the dyadic interviews to develop qualitative studies and RCTs examining the role of the caregiver on remote stroke rehabilitation outcomes.
- Please see Table 1 (below) for the outcomes with timepoints.

Primary and Secondary Outcomes with Timepoints			
Primary	Timepoint	Secondary	Timepoint
MoCA (Appendix J)	Baseline and Last Session	Pre-Intervention Questionnaire (Appendix R)	Baseline Session
Fugl-Meyer (Appendix K)	Baseline and Last Session	Therapy Follow-Up Checklist (Appendix M)	Session 2 – Last Session
ARAT (Appendix L)	Baseline and Last Session	Post-Intervention Questionnaire (Appendix S)	Last Session
Caregiver Burden Scale (for caregiver only; Appendix F)	Baseline and Last Session		
Simulator Sickness Questionnaire (Appendix I)	Session 1 – Last Session		
System Usability Scale (Appendix G)	Last Session		
Presence Questionnaire (Appendix H)	Last Session		

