Appendix A
Description of Instruments

Variables	Specific Aims	Stroke Participants	Informal Caregiver	Data Collection Procedures
		Measures/Descriptions	Measures/Descriptions	
Pre-Intervention Questionnaire (Appendix R; Secondary Outcome)		Demographic data will be collected via survey (e.g., age, sex, race, education, health history, prior technology use, etc.)	Demographic data will be collected via survey (age, sex, race, education)	Baseline (RedCap), The PI, therapist, and/ or RA will review the data with the participants)
Feasibility (Primary Outcome)	SA1	Number of sessions attended; Duration (minutes) of session	N/A	Continuous – PI, therapist, and/ or RA will maintain log
Usability (Appendix G; Primary Outcome)	SA1	The System Usability Scale (SUS) ¹ measures the impact, perceived usefulness and ease of use, and user control of the technology using a 5- point Likert scale (1= strongly agree to 5= strongly disagree) with a score range 0-100. Higher scores (>68) indicate higher perceived usability. The SUS is a widely-used 10-item validated instrument with a Cronbach's alpha of .91. ²	N/A	Post-intervention (RedCap)

Variables	Specific Aims	Stroke Participants	Informal Caregiver	Data Collection Procedures
		Measures/Descriptions	Measures/Descriptions	
Usability (Appendix H; Primary Outcome)	SA1	The Presence Questionnaire (PQ ver.3) evaluates the user's level of presence in the VR environment on a 7-point scale with 1 being the lowest and 7 the highest level of presence. The PQ is widely-used in VR research is a validated instrument with a Cronbach's alpha of .91. ³		of 87% in detecting mild cognitive impairment ⁶ .
Acceptability (Appendix I; Primary Outcome)	SA1	The Simulator Sickness Questionnaire (SSQ) ⁴ is comprised of 16 items that capture physical symptoms commonly associated with prolonged activity in a simulator. Each symptom is ranked in order of effect on the user (none, slight, moderate, severe.). The SUS is widely-used in VR research is a validated instrument with a Cronbach's alpha ranging from .84-.94 on subdimensions. ⁵		

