Cognitive Assessment (Appendix J; Primary Outcome)	SA2	The Montreal Cognitive Assessment (MOCA) is a 30-item screening tool used to detect cognitive impairment that takes 10 minutes to complete. It measures cognition measures including attention and memory. The MOCA has good evidence of internal consistency (Cronbach's alpha = .82) and test-retest reliability (r = .92) ⁶ . At a cutoff score of 26, MOCA has a sensitivity of 90% and specificity		

N/A

P
o
s
t
-
i
n
t
e
r
N/A
e
n
t
i
o
n
(
R
e
d
C
a
p
)

nuous – the participant
will be evaluated with the
SSQ by PI, therapist, or
RA before and after the
intervention

Baseline & Post-
Intervention - the PI,
therapist or RA will
conduct the cognitive
evaluation

N/A

C
o
n
t
i

Variables	Specific Aims	Stroke Participants	Informal Caregiver	Data Collection Procedures
		Measures/Descriptions	Measures/Descriptions	
Upper Limb Assessment (Appendix K; Primary Outcome)	SA2	The Fugl-Meyer Assessment-Upper Extremity ⁷ is scored on 7 domains on a 3-point scale (0 - cannot perform, 1 -performs partially, 2 - performs fully) for a total of 66 points. It is a validated instrument with a Cronbach's alpha of .88-.90. ⁸	N/A	Baseline & Post intervention – the occupational therapist and/ or RA will conduct the upper extremity assessment
Upper Limb Assessment (Fine motor) (Appendix L; Primary Outcome)	SA2	The Action Research Arm Test (ARAT) has 19 items with 4 subscales (grasp, grip, pinch, and gross movement) and arranged in order of decreasing difficulty. Scoring is recorded on a 4-point scale (0 – no movement, 1 – movement is partially performed, 2 – completed task but abnormally long amount of time, 3 – movement is normal) for a total of 57 points. It is a validated instrument Cronbach's alpha of .98. ^{9,10}	N/A	Baseline & Post intervention – the occupational therapist and/ or RA will conduct the upper extremity assessment
Caregiver Burden (Appendix F; Primary Outcome)	SA3	N/A	The Burden Scale for Family Caregivers (BSFC-s) is a 10-item questionnaire using a 4- point Likert scale (1= strongly agree to 4= strongly disagree). BSFC-s has a Cronbach's alpha of .92 and adequate evidence of convergent and discriminant validity (Giessen Symptom Complaints List-24: r = 0.68; Caregiver Strain Index: r =	

0
.7
0
;
B
e
r
l
i
n
n
v
e
n
t
o
r
y
o
f
C
a
r
e
g
i
v
e
r
s
,

B
u
r
d
e
n
w
i

th Dementia Patients: $r = 0.16$; $p < 0.001$) for

Baseline & Post- Intervention (RedCaep)

n

1

1

.

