Appendix F
Burden Scale for Family Caregivers – short version

We are asking you for information about your present situation. The present situation comprises your caregiving deduced from the illness of your family member (or friend).

The following statements often refer to the type of your assistance. This may be any kind of support up to nursing care.

Please draw an "X" for the best description of your present situation.
Please answer every question!

	strongly agree	agree	disagree	strongly disagree
1. My life satisfaction has suffered because of the care.				
2. I often feel physically exhausted.				
3. From time to time I wish I could "run away" from the situation I am in.				
4. Sometimes I don't really feel like "myself" as before.				
5. Since I have been a caregiver my financial situation has decreased.				
6. My health is affected by the care situation.				
7. The care takes a lot of my own strength.				
8. I feel torn between the demands of my environment (such as family) and the demands of the care.				
9. I am worried about my future because of the care I give.				
10. My relationships with other family members, relatives, friends and acquaintances are suffering as a result of the care.				

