Appendix G
System Usability Scale (SUS)

	Strongly Disagree	Disagree	Neither Agree nor Disagree	Agree	Strongly Agree
I think that I would like to use this headset frequently					
I found this headset unnecessarily complex					
I thought this headset was easy to use					
I think that I would need assistance to be able to use this VR experience					
I found the various functions in this headset were well integrated					
I thought there was too much inconsistency in the headset					
I would imagine that most people would learn to use this headset very quickly					
I found the headset very cumbersome/awkward to use					
I feel confident using the headset					
I needed to learn a lot of things before I could get going with this headset					

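### Do the printed response codes for the usability scale (SUS) and the caregiver burden scale (BSFC-s) leave scores open to being read backwards?

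*Combined protocol and SAP*

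**What the plan says.** For the SUS, Appendix A (Usability row) states the item codes, the range and the direction of the total: "1= strongly agree to 5= strongly disagree) with a score range 0-100. Higher scores (>68) indicate higher perceived usability". The form in Appendix G shows five unnumbered options running from strong disagreement on the left to strong agreement on the right. Its ten items alternate in polarity; item 2, for example, is "I found this headset unnecessarily complex" and item 3 is "I thought this headset was easy to use". Under S.A.1 of the Statistical Analysis section the SUS is summarised descriptively: "participant scores on the SUS and PQ will be calculated". No item key is printed.

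For the BSFC-s, Appendix A (Caregiver Burden row) describes a "10-item questionnaire using a 4- point Likert scale (1= strongly agree to 4= strongly disagree". All ten items in Appendix F state burden; the first is "My life satisfaction has suffered because of the care". The same row of Appendix A reports validity correlations: "Giessen Symptom Complaints List-24: r = 0.68; Caregiver Strain Index: r", the second being 0.70. Under S.A.2 the analysis is that "standardized differences in the BSFC-s scores will provide the effect sizes for the change in caregiver burden". No legible text gives the rule for the total, its direction or the order of subtraction, although the end of that table cell is damaged in the text available.

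Table 1 lists both scales as primary.

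**The concern.** The only SUS codes in the plan run against the order in which the options appear on the form. With half the items worded each way, the total means nothing until one half is reversed, so codes and key must agree. If data were captured left to right as 1 to 5 and scored with a key built for Appendix A's codes, or the other way round, every participant's usability would be mirrored. The spread of the scores would be unchanged and would give no warning.

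The BSFC-s raises a sign question. On a scale named for burden, a plain sum of the printed codes is lowest when burden is highest. A reader who takes a negative standardized difference to mean relief would then have it backwards. The plan intends its results to inform later randomized trials and work on caregiver burden, so a reversed sign could travel.

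**Working it through.** **SUS inputs.** Ten items, five of each polarity (Appendix G); codes y from 1 (strongly agree) to 5 (strongly disagree), total 0 to 100, higher is better (Appendix A). Assumption, because no key is printed: items carry equal weight, each contributes 0 to 4, and the sum is multiplied by 2.5.

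1. *Can Appendix A's codes give the stated range and direction?* Score favourable items as 5 − y and unfavourable items as y − 1. The best possible user answers y = 1 on favourable items and y = 5 on unfavourable ones: 2.5 × (5 × 4 + 5 × 4) = 100. The worst possible user scores 2.5 × 0 = 0. The stated range and direction are reproduced.

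2. *Does left-to-right coding give the same result?* Let x = 6 − y, so that 1 is strong disagreement. With x − 1 for favourable and 5 − x for unfavourable items, each contribution equals the one in step 1, so the total is identical. Either coding is sound with its own key.

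3. *What does a mismatch do?* Apply the step 2 key to y. Favourable items give y − 1 = 4 − (5 − y), and unfavourable items give 5 − y = 4 − (y − 1). Every item becomes 4 minus its correct contribution, so the total is 2.5 × 40 − S = 100 − S. Hence 80 becomes 20, 75 becomes 25, and the benchmark value 68 becomes 32. The identity held in all of 10,000 random response sets.

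4. *Could the plan intend an unkeyed sum?* No. Ten codes of 1 to 5 add up to between 10 and 50, not 0 to 100. The best and worst users would also tie: 5 × 5 + 5 × 1 = 30 and 5 × 1 + 5 × 5 = 30.

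**BSFC-s inputs.** Ten burden-worded items (Appendix F); codes 1 (strongly agree) to 4 (strongly disagree) (Appendix A). The plain sum is an assumption; the plan does not prescribe it.

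5. *Range.* Maximum burden gives 10 × 1 = 10 and minimum burden 10 × 4 = 40. Reversing each item as 5 − y turns a total T into 50 − T.

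6. *Change.* If a caregiver moves from agree to strongly agree on five items, the printed codes go from 20 to 15 (−5) and the reversed codes from 30 to 35 (+5).

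7. *Effect size.* Reversal negates every difference and leaves the SD alone, so d changes sign only. With eight made-up differences (−5, −3, −4, 0, 1, −2, −6, −1), the mean is −20/8 = −2.5, the SD is √(42/7) = 2.45 and d = −1.02; reversed, d = +1.02.

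8. *Which direction do the documents suggest?* If the complaints list and the strain index rise with complaints and strain, the reported correlations of 0.68 and 0.70 belong to a score that rises with burden. That points an analyst away from the plain sum of the printed codes.

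**The case for a change.** The best case for a change is that both scales are primary, that Appendix A makes direction plain for the Presence Questionnaire, the Fugl-Meyer and the ARAT but not for the BSFC-s, and that the same appendix contains a visible slip (its simulator sickness row names the SUS by mistake). A few lines would close the gap, and a burden effect with the wrong sign could mislead the design of the next trial.

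Much of this is accurate. The SUS key is not reprinted, and no legible text fixes the BSFC-s direction or the order of subtraction. What does not stand is the step from there to a wrong result. For the SUS, the direction of the total is stated, and what is called a conflict compares numeric codes with the layout of an unnumbered form; a database choice can carry any code wherever it sits on the screen. Mirrored scores need a further error, a key that does not fit the codes, and nothing in the documents shows one. For the BSFC-s, the backwards reading needs an unprescribed plain sum and a reader who ignores the printed codes.

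Recoding could itself do harm. The proposed timeline in Appendix P puts data collection in February to May, within a schedule running December 2022 to November 2023, and this version is dated 03/06/2024. Data may therefore already exist, and altering codes part-way could create the very mixture that is feared. The key used above is also an assumption that cannot be confirmed from these documents, so it is not text to insert.

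**Conclusion.** The concern does not call for a change. With codes and key matched, the SUS error is zero; a mismatch would turn S into 100 − S, but none is documented. The SUS analysis is descriptive, and the value 68 is an interpretive benchmark, not a success criterion. For the BSFC-s the most that can happen is a mislabelled sign; the size of d is untouched, and the plan says that inference is not its main interest. Sample size is unaffected, and any slip can be corrected by a fixed recode of item responses.

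What remains is a scoring key and a sign convention that the plan leaves to two named instruments, for which it cites published sources. An analyst would settle both when scoring and would state the direction when reporting the burden change.

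This rests on three assumptions: an equal-weight SUS key scaled to the stated range, item-level responses being kept in REDCap, and nothing contrary in the damaged end of the BSFC-s cell. The database codes are not shown, so correct scoring is not proven; equally, the plan as written does not lead to a wrong score.

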Appendix I
Simulator Sickness Questionnaire (SSQ)

Simulator Sickness Questionnaire (SSQ) items

SSQ items	Likert Scale		
	Slight	Moderate	Severe
General Discomfort			
Fatigue			
Headache			
Eyestrain			
Difficulty Focusing			
Increased Salivation			
Sweating			
Nausea			
Difficulty Concentration			
Fullness of Head			
Blurred Vision			
Dizziness (eye open)			
Dizziness (eye closed)			
Vertigo			
Stomach Awareness			
Burping			

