 Arrange sessions schedules with Dyads for the length of the study (2 sessions/week each being an hour minimum in length). Reserve smart room for duration of study.	

 _ Complete the Pre-Intervention Questionnaire (Secondary Outcome; Appendix R) 	

 _ Have the stroke survivor complete the Simulator Sickness Questionnaire (SSQ) at the beginning and end of the first 1-hour session (Primary Outcome; Appendix I) 	
2nd Session (Week 1)	Initial & Date completed

 _ Research Assistant complete the Therapy Follow Up Checklist with Subject before the start of the session. (Secondary Outcome; Appendix M) 	

 _ Have the stroke survivor complete the Simulator Sickness Questionnaire (SSQ) at the beginning and end of the second 1-hour session (Primary Outcome; Appendix I) 	
3rd Session (Week 1)	Initial & Date completed

 Research Assistant complete the Therapy Follow Up Checklist with Subject before the start of the session. (Secondary Outcome; Appendix M) 	

 Have the stroke survivor complete the Simulator Sickness Questionnaire (SSQ) at the beginning and end of the third 1-hour session (Primary Outcome; Appendix I) 	
4th Session (Week 2)	Initial & Date completed

 Research Assistant complete the Therapy Follow Up Checklist with Subject before the start of the session. (Secondary Outcome; Appendix M) 	

 Have the stroke survivor complete the Simulator Sickness Questionnaire (SSQ) at the beginning and end of the fourth 1-hour session (Primary Outcome; Appendix I) 	
5th Session (Week 2)	Initial & Date completed

 Research Assistant complete the Therapy Follow Up Checklist with Subject before the start of the session. (Secondary Outcome; Appendix M) 	

 Have the stroke survivor complete the Simulator Sickness Questionnaire (SSQ) at the beginning and end of the fifth 1-hour session (Primary Outcome; Appendix I) 	
6th Session (Week 2)	Initial & Date completed

 Research Assistant complete the Therapy Follow Up Checklist with Subject before the start of the session. (Secondary Outcome; Appendix M) 	

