We will give the stroke survivor the Montreal Cognitive Assessment (MoCA) that will assess their cognitive capabilities. We will arrange a time to meet with them on a video call using the computer and this will take only 15 or 20 minutes.	
1. Cognition (MoCA) test completed (Primary Outcome; Appendix J)	
12th Session (Week 4, last session; in the event that the study participant and/ or caregiver are unable to complete any post-intervention items, we will request a video call to complete any missing items that were not completed on the last session at a time convenient to the stroke participant or caregiver)	Initial & Date completed

 _____ Research Assistant complete the Therapy Follow Up Checklist with Subject before the start of the session. (Secondary Outcome, Appendix M) _____ Have the stroke survivor complete the Simulator Sickness Questionnaire (SSQ) at the beginning and end of the last 1-hour session (Primary Outcome; Appendix I) _____ Complete the System Usability Survey (SUS) via REDCap (Primary Outcome; Appendix G) _____ Complete the Presence Questionnaire (PQ) (Primary Outcome; Appendix H) 	

 Complete the Cognition (MoCA) test (post-intervention, if not completed during the Pre-Last Visit) (Primary Outcome; Appendix J)	
 Complete the Fugl-Meyer Upper Extremity Assessment (post-intervention) (Primary Outcome; Appendix K)	
 Complete the Action Research Atm Test (ARAT) (post-intervention) (Primary Outcome; Appendix L)	
 Complete the Caregiver Burden Questionnaire (Primary Outcome; Appendix F)	
 Complete the Post-Intervention Questionnaire (Participant and Caregiver) (Secondary Outcome; Appendix S)	

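### The SSQ form as reproduced cannot record an absent symptom, and the plan has no rule for blank lines on this primary acceptability measure

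*Combined protocol and SAP*

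**What the plan says.** Appendix A describes the SSQ as an instrument that "is comprised of 16 items that capture physical symptoms". Its response scale has four levels: "Each symptom is ranked in order of effect on the user (none, slight, moderate, severe"). The row label gives its role: "Acceptability (Appendix I; Primary Outcome"). Table 1 in the Outcomes section also lists it as primary.

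The Appendix I form carries 16 symptom lines, but its response columns read only "Slight Moderate Severe". It does not say what to do when a symptom is absent.

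The Statistical Analysis section plans the following: "Descriptive statistics for scores on the SSQ will be calculated at baseline and after each session". It adds: "We will examine the trend of symptoms for each participant". It does not give numeric codes for the responses, a total or subscale formula, or a rule for unmarked lines.

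Appendix Q sets the frequency: "Have the stroke survivor complete the Simulator Sickness Questionnaire (SSQ) at the beginning and end of the first 1-hour session". The same entry recurs for every session up to the "12th Session (Week 4, last session").

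**The concern.** The definition of the instrument and the form printed for it disagree on the lowest response level. With the form as reproduced, a survivor without a given symptom has two options: leave the line empty or mark *Slight*. In the first case, an empty line has two meanings, no symptom and no answer, and nothing written separates them. In the second case, a true zero is recorded as a symptom.

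The two errors run in opposite directions. Skipped lines read as *none* can understate sickness, and symptom-free lines marked *Slight* overstate it. If staff or survivors differ in how they use blanks, or change over the four weeks, a participant's trend can move without any change in symptoms.

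*None* should be a common answer. Eligibility excludes people with a history of motion sickness, vertigo or dizziness, and half of the forms are filled in before the headset goes on.

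**Working it through.** The plan states no figure on this point, so there is nothing to reproduce. The check compares the texts and then shows how large the effect could be under stated assumptions.

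**Comparison**
- Number of items: Appendix A says 16 and Appendix I prints 16. They agree.
- Response levels: Appendix A has 4 and Appendix I has 3. The level that is missing is the lowest.
- Rule for blanks: none is given for the SSQ. Two other forms do have one. The caregiver burden scale (Appendix F) asks for an answer to every item, and the medical history block in Appendix R asks respondents to mark only what applies. The SSQ form has neither instruction.

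**Volume**
- Inputs: 20 survivors (Recruitment), 12 sessions and 2 forms per session (Appendix Q), 16 items (Appendices A and I).
- Per survivor: 12 × 2 × 16 = 384 item cells.
- All survivors at full attendance: 20 × 12 × 2 = 480 forms, and 480 × 16 = 7,680 cells.
- At the 8-session minimum in the Statistical Analysis section: 20 × 8 × 2 = 320 forms, and 320 × 16 = 5,120 cells.

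Not every cell is affected. A line marked moderate or severe is unambiguous.

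**Blanks.** Let *s* be the chance that an item is skipped, assumed independent across items. The chance that a form has at least one skipped item is 1 − (1 − *s*)^16, and the expected number of skipped cells at full attendance is 7,680 × *s*. The documents give no value of *s*, so a range is shown.

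| *s* (assumed) | Forms with at least one skip | Skipped cells |
|---|---|---|
| 1% | 14.9% | 77 |
| 2% | 27.6% | 154 |
| 5% | 56.0% | 384 |
| 10% | 81.5% | 768 |

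These are cells that could not be told apart from *none*. They are not all wrong scores, because a skipped line on which the symptom was in fact absent would be read correctly by luck.

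**Marking *Slight* for an absent symptom.** Assume codes 0 to 3 and an unweighted sum, since the plan gives no scoring. With a *None* column the sum runs from 0 to 16 × 3 = 48. With three columns and every line marked, it runs from 16 × 1 = 16 to 48. If a share *q* of the lines on a symptom-free form is marked *Slight*, the sum rises by 16 × *q*:
- *q* = 10%: 1.6 points
- *q* = 25%: 4 points
- *q* = 50%: 8 points
- *q* = 100%: 16 points, or 16/48 = 33% of the maximum

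The share *q* is also an assumption.

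**The case against.** **The column may have been lost in reproduction.** This is the most serious objection. The Fugl-Meyer form in Appendix K shows that it can happen: sections III and IV each list three items with a maximum of 6, which needs a top score of 2 per item, yet only the *none* and *partial* headings appear. There, however, the last column is gone. In Appendix I the first option is absent and the rest of the grid is regular, and the response grids in Appendices F and G came through complete. The mismatch stands, but subject to a look at the source page.

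**Appendix I may not be the form in use.** It has no field for participant, date, session or before/after. The Pre-Screening and Measurements section says that the quantitative measures are accessible through REDCap, so an electronic version may already include *None*. This also stands, as a reason to check that build first.

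**Staff are involved.** Appendix A has the investigator, therapist or research assistant evaluate the participant with the SSQ, although Appendix Q has the survivor complete it. With staff at hand, blank as *none* is a natural convention. It is not written down.

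**A constant shift drops out of a trend.** This holds for lines that stay symptom-free. If absent symptoms are marked *Slight*, though, a real move from absent to slight scores 1 − 1 = 0 instead of 1 − 0 = 1. The plan also summarises the scores themselves, not only changes.

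**Skipping may be rare.** A reader might infer that skipped lines are likely because the sample is selected for cognitive impairment. The documents do not support this: the eligibility text also admits survivors with normal cognition and a qualifying Fugl-Meyer score, and no skip rate is given.

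**Conclusion.** The inconsistency holds, subject to the source page and the REDCap build. As reproduced, the form for the primary acceptability measure cannot record its own lowest level. Without a coding or blank rule, *none* cannot be told from *not answered*, and a symptom-free line could be marked *Slight*.

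The size of the effect is unknown. The skip rates and marking shares in the working are illustrations, and 7,680 cells is reached only if all 20 survivors attend all 12 sessions.

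A reader might go further and infer that the acceptability outcome is corrupted, or that symptom-free survivors are in practice pushed to *Slight*. The documents show neither. They show an ambiguity, not how staff and survivors handled it.

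Priority is moderate, not must-fix. The SSQ analysis is descriptive, with no threshold, test or progression rule. The instruction to stop a session depends on symptoms or the participant's wish, not on an SSQ score. The closing interview (Appendix S) also asks about symptoms that would deter further use.

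**What to change.** 1. Check the source page of Appendix I and the REDCap build. If both already offer *None*, correct the appendix, and add the coding and missing-item rule to the Statistical Analysis section.
2. If *None* is absent, add a *None* (= 0) column to the paper and electronic forms. Require one mark on each of the 16 lines, with staff checking this at each administration. From then on, treat an unmarked line as missing.
3. State the item codes, the score to be computed, and how a form with missing items is handled.
4. The version date (03/06/2024) falls after the stated study period ended (October 2023), so completed forms may exist. For these, document how staff used blanks. Where blank meant *none*, take that as the main reading. Report the number of blank lines per administration, and show the alternative handling as a sensitivity analysis. Do not make missing the default for old blanks: if blank meant *none*, that would discard true zeros and inflate the SSQ means.

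The cost is one column, a few sentences in the analysis section, and a brief check of each form. Existing data need one count of blanks and one extra tabulation. What cannot be recovered later is the meaning of old blanks if nobody records the practice now.
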